5.1 Scientific background and relevance

The dramatic increase in human life expectancy in the last 60 years has been driven by reduced deaths of people in their 60s and 70s, leading to demographic shifts so that most populations globally are characterised by increasing numbers of elderly adults. However, an increasing number of these extra years of life are spent in poor health with more years spent in care facilities due to reduced ability to live independently. Osteoporosis is a major contributor to loss of independence due to bone fractures and resulting hospital treatments lead to significant morbidity. Even after successful fracture treatment, independent living is compromised in many patients. While drug treatments reduce consequences of osteoporosis significantly, there is a pressing need for non-pharmacological interventions to improve bone health across the life-course and to reduce likelihood of age-related bone disease.

The skeleton has protective, mechanical and metabolic roles, providing structural support and acting as a site for mineral storage (Seeman et al., 2006). Bone turnover, the cellular machinery responsible for bone integrity and strength, is a finely balanced process that is responsive to hormones and mechanical loading.

Physical activity is beneficial for the skeleton acting through the process of functional adaptation, a process that is less effective in older animals and humans than younger ones (Samvelyan et al., 2021). In addition, older people and those with bone loss, who are already at increased risk of fractures, may be

unable to perform exercise that is sufficiently vigorous to strengthen their bones. Therefore, there is a need to identify the most effective ways to exercise with maximal benefits to the musculoskeletal system.

Exercise is a non-pharmacological intervention that can modify bone turnover, improve bone health and reduce the risk of osteoporosis in later life (Bonnet and Ferrari, 2010). Mechanical loads that are produced by exercise change local microenvironments of the canicular networks within the bone framework via dynamic fluid shifts stimulating local osteocytes and ultimately bone turnover (Schaffler et al., 2012; Klein-Nulend et al., 2013).

The complex and coordinated relationship between the endocrine regulation of energy metabolism, adipose tissue, and bone homeostasis has been studied extensively (De Paula et al., 2013). Concentrations of hormones, including insulin and amylin, change profoundly in anticipation of, during or after eating (preprandial, prandial, and postprandial responses). These hormones have potential anabolic effects on bone homeostasis, therefore, synergies between endocrine and mechanical effects could alter the bone turnover response to exercise.

The measurement of bone turnover markers, such as procollagen type 1 N-terminal propeptide (P1NP) and CTX, allow to assess the dynamic fluctuations in metabolic activity of bone (Delmas et al., 2006). Prolonged endurance exercise increases CTX (Guillemant et al., 2004; Hermann et al., 2007; Kerschan-Schindl et al., 2009; Maïmoun et al., 2006; Scott et al., 2010) but bone formation markers are largely unresponsive (Guillemant et al., 2004; Hermann et al., 2007; Maimoun et al., 2006; Scott et al., 2010). This suggests that prolonged exercise might result in a transient negative bone remodelling balance and this acute response may be implicated in changes in bone mineral density with repeated exercise over time in some sub-groups. However, the response of bone turnover markers to exercise is highly variable and appears to be modality-, intensity-, age- and sex-specific.

Feeding modulates the metabolic responses to prolonged exercise. The metabolic adaptations to fuel supply when fed and with fasting are well studied, however, there is limited consideration of the effect of these practices on other biological responses to exercise, such as bone metabolism. Fasting attenuates the circadian variation in CTX, a marker of bone resorption, whilst feeding suppresses resting CTX within 1-hour and concentrations are decreased by around 50% after 2–3 hours (Bjarnason et al., 2002; Henriksen et al., 2003; Holst et al., 2007). In contrast, and in line with the response to exercise, bone

formation is largely unresponsive to nutrient ingestion (Bjarnason et al., 2002; Henriksen et al., 2003; Holst et al., 2007). Concentrations of hormones including insulin and parathyroid hormone (PTH) change profoundly across pre-prandial, prandial, and postprandial states. These hormones have potential anabolic effects on bone homeostasis, therefore, synergies between endocrine and mechanical effects could alter the bone turnover response to exercise.

Despite the reported independent effects of feeding and exercise on bone metabolism, only a limited number of studies in humans have investigated how feeding and fasting practices mediate the effects of endurance exercise on bone metabolism, with mixed findings (Borer et al 2019; Scott et al., 2012). Existing studies in this area have largely been carried out on athletes (Scott et al., 2012) or populations suffering from different disease states, such as T1 and T2 diabetes (Borer et al., 2019). Previous studies have also not always used a comparator/control arms (Scott et al., 2012).

The flat running protocol used in previous studies (Scott et al., 2012) may also not be optimal to induce enough strain on bone for bone turnover markers to fully respond and therefore in designing the study, mechanical skeletal loading will be enhanced by using a downhill treadmill running protocol. The idea regarding loading is based on a study where running at 3 m/sec at a 6° decline increased ground reaction force (GRF) by 24.3%, while running on a +6° incline reduced it by 22% relative to exercise on level surface (Gottschall and Kram, 2005). This proof-of-concept study will investigate the effect of an overnight fast versus feeding of a single mixed meal, on the acute changes in bone turnover markers to a bout of treadmill running in healthy young adults.

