6.4 Methods

6.4.1 VO₂Max and determination of running speed

Participants will perform a two-stage graded exercise test on a treadmill to determine the speed of downhill running that elicits 70% VO_{2max}. For the first stage, VO_{2max} will be determined via a graded exercise test. The test will begin with participants completing a 4-min warmup at 4.8km/h, followed by 1 minute of passive rest. The graded exercise test will start between 8.0 and 9.6 km/h, with the velocity increasing by 1.6km/h every 2 mins until reaching a speed of 14.4km/h. At this point, incline will be increased by 2% every 2 mins until the participant reaches volitional exhaustion (Succi et al. 2022). Heart rate and rate of perceived exertion (RPE) will be recorded via heart rate monitor (Garmin HRM-Dual, Garmin, KS, USA) and RPE Scale (Borg, 1982), to confirm maximal effort. Expired air will be collected and the gas exchange will be analysed using the Metelyzer 3B (Cortex, Leipzig, Germany). The equipment will be calibrated prior to each test as per manufacturer's directions using standard gases.

The second stage of the treadmill test will be used to determine the running speed that elicits 70% VO_{2peak} at a decline of -6%. Participants will start running at the same speed as the first test. Speed will be increased by 1km every 2 mins for five stages. Regression analysis will then be performed to determine the speed that elicited 70% VO_{2max}. Participants will then rest for 30 minutes.

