6.4.3 Downhill running protocol

Participants will perform 45 min of treadmill running at 70% $VO_{2\max}$ at a -6% slope, one and half hours after a standardised breakfast (FED) or fasted (FAST). Downhill treadmill slope will increase Ground Reaction Forces (GRFs) relative to level walking (Gotschall and Kram, 2005).

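### Does quoting a loading gain measured at a 6-degree decline undermine a trial that runs its participants at a -6% slope?

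*Combined protocol and SAP*

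**What the plan says.** Section 5.1 argues that flat running may strain bone too little for turnover markers to respond fully, and so "mechanical skeletal loading will be enhanced by using a downhill treadmill running protocol". Its only quantitative support is a study in which "running at 3 m/sec at a 6° decline increased ground reaction force (GRF) by 24.3" per cent relative to exercise on the level.

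The methods give the decline as a percentage. In section 6.4.1 running speed is found "at a decline of -6" per cent, and "Regression analysis will then be performed to determine the speed that elicited 70" per cent of maximal oxygen uptake. Section 6.4.3 specifies the 45-minute experimental run "at a -6% slope, one and half hours after a standardised breakfast (FED) or fasted (FAST". The same section cites the ground reaction force study again, but only for direction: "Downhill treadmill slope will increase Ground Reaction Forces (GRFs) relative to level walking". Percentages are also used for the incline steps of the maximal test ("incline will be increased by 2% every 2 mins"). Degrees appear only in the rationale.

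**The concern.** The number 6 appears in both places with different units, and no conversion is given. Read quickly, the protocol seems to promise about a quarter more ground reaction force than level exercise, yet the slope it specifies is much shallower than the one that produced that figure. Speed differs too: the cited study ran at a fixed 3 m/s, while here it is set for each participant. The comparator also shifts, from exercise on a level surface in section 5.1 to level walking in section 6.4.3.

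Section 4 frames the aim around an adequate mechanical stimulus, and downhill loading is the stated improvement on earlier flat-running work. If the added loading were much smaller than readers suppose, they might credit the trial with a stimulus it did not apply. They might also be unable to tell whether a null result reflects feeding or weak loading.

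**Working it through.** **Inputs.** Cited decline 6 degrees, speed 3 m/s, rise in ground reaction force 24.3% (section 5.1). Trial slope -6% (sections 6.4.1 and 6.4.3). Start speed 8.0 to 9.6 km/h, with five stages rising by 1 km/h (section 6.4.1, reading its 1 km step as 1 km/h). The plan states no loading figure for its own run, so there is none to reproduce.

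**Units.**
- Angle of a 6% grade: arctan(0.06) = 3.43 degrees (3.44 if grade is defined by the sine).
- Grade of a 6-degree decline: tan(6°) = 0.105, or 10.5%.
- Ratio of angles: 3.43 / 6 = 0.57. Ratio of grades: 6 / 10.5 = 0.57.

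The mismatch is real, and the conversion is not in dispute.

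**Can it be turned into a loading shortfall?** Strict proportionality to angle would give 24.3 × 3.434 / 6 = 13.9%. The documents do not support proportionality, and the calculation ignores speed. The cited 3 m/s is 3 × 3.6 = 10.8 km/h. Five stages starting at 8.0 km/h reach 8.0 + 4 = 12.0; starting at 9.6 km/h they reach 9.6 + 4 = 13.6. The speeds tested thus lie on both sides of 10.8 km/h. With slope and speed both different, neither the size nor the direction of the net departure from 24.3% can be derived. The 13.9% should not be used.

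**Where does the 24.3% go?**
- *Sample size (section 6.2).* The inputs are a CTX difference of 0.168 µg/l, SD 0.2 µg/l, 80% power and a two-sided 2.5% level. The paired normal approximation gives n = [(2.241 + 0.842) × 0.2 / 0.168]² = 13.5, so 14, plus 2 for withdrawals = 16, as stated. (A t-based calculation asks for 17 before withdrawals, a separate matter in which slope plays no part.) The difference is based on the earlier fasting-versus-feeding study, which section 5.1 describes as flat running, so power assumes no downhill gain.
- *Measurements (sections 6.3 and 6.8).* Ground reaction force is not measured.
- *Model (section 6.9).* Fixed effects are condition and time point; loading is not a term.

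**Is the primary contrast affected?** Write f_FAST(L) and f_FED(L) for a participant's CTX change at loading L. The primary outcome compares f_FAST(L) with f_FED(L) at the same slope and the same individual speed, within participant. A different L may change the size of the effect being estimated, but it does not favour one condition.

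**Do the operating instructions conflict?** Speed determination and the experimental run both specify -6%, and the familiarisation section refers to the same protocol. Staff following the methods meet a single setting.

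**The case for a change.** The strongest case for acting is that the cited study is the only quantitative reason given for going downhill. With no ground reaction force measurement and no level-running arm, the trial cannot show afterwards what extra loading it delivered. Section 11 says the data will feed a wider programme, so a misattributed figure could carry forward, and correcting the text costs almost nothing.

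Part of this stands. The 24.3% must not be quoted as the stimulus delivered here, and the documents do not settle whether the degree or the percentage reflects the intention.

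The consequence claimed for a null result does not stand:
- The ambiguity about loading comes from not measuring force. It would remain if every section used the same unit.
- The adequate stimulus in section 4 is not tied to 24.3% or to any force threshold.
- The breakfast-only condition, sampled at matching times, lets fed exercise be compared with no exercise, so the trial can see whether the bout moved the markers in the fed state. It does not isolate the downhill component, but no choice of unit would.
- Section 5.1 reports that feeding alone lowers resting CTX by around 50% after 2 to 3 hours, so a fasted-versus-fed difference does not depend on loading alone.

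Section 5.1 also presents the study as the origin of an idea ("The idea regarding loading is based on a study where running at 3 m/sec at a 6° decline" and so on), not as a forecast. Citing work done at another slope and speed is ordinary background.

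**Conclusion.** The mismatch is genuine but editorial. The specified slope is 3.43 degrees against a cited 6 degrees, a ratio of 0.57; the effect on ground reaction force cannot be quantified from the documents. The effect on sample size is nil, no model term depends on the figure, and the primary contrast is not biased. Removing the mismatch would alter rationale wording and no result, so no change to design or analysis is called for. Sections 5.1, 6.4.1 and 6.4.3 should be reconciled as a matter of wording on unit, comparator and the status of the 24.3%. Which decline is intended is for the investigators, and nothing here bears on that choice.

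This rests on two assumptions: that staff set the treadmill from the methods sections, and that each participant runs at one slope on both exercise visits. If the slope differed between a participant's fasted and fed visits, the within-participant comparison would no longer hold loading constant and the conclusion would need to be revisited. Nothing in the methods points that way.

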5.2 Study rationale

Since dietary interventions are associated with healthy ageing (Kalache et al, 2019), a combination of exercise and nutrition may benefit bone health in ageing by utilising synergies between osteotropic influences. There is already support for this idea. The data from Samvelyan et al (2021) latest study on model organisms provides evidence that the effects of anabolic hormones in increasing bone formation in response to mechanical loading may be manipulated by changing timing of feeding in relation to exercise imposition (Samvelyan et al, 2021). There are already widespread fasting and caloric restriction interventions in use in humans for weight control and for healthy ageing. For instance, the 5:2 diet in which food intake is restricted to 500–600 calories on 2 days per week, which could be exploited to provide fasting experienced by animal models in Samvelyan et al (2021) study before eating and then exercising. It has also been shown that in diabetic postmenopausal women there is a significant increase

in bone osteogenic response (defined as the ratio of osteogenic C-terminal propeptide of type I collagen (CICP) over bone-resorptive CTX markers) when exercise followed a meal but not when it preceded a meal (Borer et al., 2019). Further, bone turnover markers and clinical risk factors can be used to identify patients at risk of osteoporotic fracture as well as those who have secondary osteoporosis (Clowes and Eastell, 2000).

5.3 Clinical relevance

Osteoporosis is a major contributor to loss of independence due to bone fractures and resulting hospital treatments lead to significant morbidity. While pharmacological treatments can reduce consequences of osteoporosis, there is a pressing need for non-pharmacological interventions to improve bone health across the life-course and to reduce likelihood of age-related bone disease.

This study will allow us to determine whether synergistic potentiating effects on bone metabolism are observed in humans in relation to the timing of food ingestion and what recommendations can be made to people with respect to food ingestion and exercise to obtain the maximal bone benefits from aerobic exercise. Furthermore, if we can identify interventions that potentiate bone's response to aerobic exercise in younger adults, then such interventions may have the ability to maximise bone mass in younger adults so that with ageing, the additional bone mineral density and improved bone microarchitecture would extend the time before osteoporotic "fracture thresholds" are reached. Therefore, understanding the bone metabolic response to exercise following fasting and feeding in younger adults is important.

[figure not shown]
Section 6: Plan of investigation

6.1. Study design

In this proof-of-concept study, sixteen young adult men (age: 28 ± 4) will be recruited in good physical condition. This will be a three-arm randomised cross-over study with a 1-week washout period between visits (**Figure 1**). Participants will be exercised following a 12-hour overnight fast (FAST) and exercised 90 minutes after a meal (FED) to test the temporal sensitivity of the loaded bone to absorbed nutrients. Participants will also attend a breakfast-only arm (without the exercise protocol). The meal will consist of 60% carbohydrate, 25% fat and 15% protein. The exercise will be a downhill running protocol adapted from previous studies in this area (Scott, 2012; Borer, 2019). Counterbalancing measures will be put in place to prevent and minimise order effects.

Participants will undergo a baseline assessment for health history (PAR-Q). Baseline measurements of weight, height, BMI and maximal oxygen uptake as well as baseline bone mineral density and body composition scans of participants will be performed with a dual energy X-ray absorptiometry (DXA) to characterise the study sample.

Figure 1: Study Design

6.2 Power calculation

The primary outcome of this study is the difference in change in CTX concentration between the pre-exercise and 2-hour post-exercise timepoints between the fasted-exercised and fed-exercised arms.

Based on changes in CTX from a previous study (Scott et al., 2012), we designated 30% as a minimally significant difference and that 30% would be approximately 0.168 µg/l. We calculated a standard deviation of 0.2 µg/l based on results from our previous studies with serial measurements of CTX. To achieve 80% power for demonstrating this mean difference as statistically significant at the 2.5% two-sided level requires a total of 16 participants (including 2 additional participants for withdrawals). This sample size is in line with that of other studies in this area.

6.3 Study measurements

The blood samples will be collected (10ml) by cannula at baseline, immediately pre-exercise, and after 15 minutes and 45 minutes of exercise and after 2-hours of recovery. The osteogenic response to exercise will be determined by measuring a marker of bone formation; P1NP and a marker of resorption; CTX-1.

To assist in making inferences on the possible hormonal interactions with mechanical, cardiovascular, and psychological stress in our study, and thus their contribution to changes in bone markers, we will also measure plasma concentrations of cortisol; a marker of physiological and psychological stress and because of its promotion of bone resorption. Insulin and glucose measurements will allow us to assess the change of concentrations in fasted and fed states. Urine samples will be collected at baseline, immediately before and after the exercise. Samples will be frozen at -80°C and analysed for bone turnover biomarkers later with the permission of participants.

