- To compare the effect of exercise on bone turnover markers before and after the meals following overnight fast in young adult male participants
- To assess the synergistic effects of feeding in addition to exercise on bone formation and resorption biomarkers in young adult male participants
- To determine the concurrent role of osteotropic hormone insulin in bone homeostasis in young adult male participants

Section 5: Background and rationale

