6.4.5 Bone turnover markers, cortisol, insulin and glucose measurements

Blood samples (around 10ml) will be collected into serum-separation tubes containing spray-coated silica and polymer gel for serum separation (BD Vacutainer venous serum separation tubes: Hemogard, Fisher Scientific, UK) for determination of bone turnover markers PINP and CTX-1. Measurements of bone turnover markers will be done at Bone Biochemistry Laboratory (The University of Sheffield, UK). Measurement of glucose, insulin, and cortisol will be done at the Chemical Chemistry laboratory (Sheffield Teaching Hospitals, UK).

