6.4.6 Sample handling

Samples will be collected into Serum Separating Tubes (SST). Blood in SST tubes will be left to clot for 15-30 minutes at room temperature and centrifuged at 2000 g for 10 minutes. The serum will be aliquoted and stored at -80⁰C until analysis.

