6.8 Outcome measures and participant involvement at each visit

All participants will be required to attend the Advanced Wellbeing Research Centre (AWRC) on four separate occasions.

At the **familiarisation visit** each participant will give informed consent. Consenting participants will complete a PAR-Q, undergo a $VO_{2\text{max}}$ test, and DXA scan to measure baseline bone mineral density and body composition. Baseline anthropometric measures, including height, weight, and BMI will be taken. Participants will be asked to follow a standardised diet three days prior to their second study visit. Participants will also be asked to refrain from strenuous physical activity during this period and will be asked to record their food and drink consumption in a diet diary.

At the **second visit**, each participant will arrive after a 12-hour overnight fast.

Counterbalancing measures will be used to assign participants to either the FASTED-exercised, FED-exercised or breakfast only conditions. During the FED-exercised or breakfast only arms, a standardised breakfast will be given at 8.30am. Exercise in the FED condition will take place 1.5 hours after breakfast has been administered (10.00am). When in the fasted condition, participants will also begin exercise at 10.00am.

Blood samples will be taken by cannulation for bone turnover marker measurement and hormone measurement at baseline (8.30am), pre-exercise (immediately before exercise), 15 minutes during exercise, 45 minutes (immediately post-exercise) and 2 hours post-exercise. Timings will also be consistent in the breakfast-only arm.

At the **third and fourth visits**, following crossover periods, participants will be assigned to the alternative conditions and study measurements repeated as per second visit.

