6.9 Statistical analysis

Normality will be assumed if Shapiro-Wilk test is not statistically significant ($P > 0.05$). Where data is normally distributed, the data will be presented as mean and standard deviation (SD). Where data were not normally distributed, data will be presented as median and IQR.

Biochemical data will be analysed using a linear, mixed model (LMM), with factors 'condition' and 'time point' as fixed effects and 'participants' as a random, within-group effect. The assumptions of the LMM (homogeneity of variance and normality) will be investigated by examining the distribution of residuals and the pattern of residuals versus fitted values. Where non-normality or non-constant variance are observed, a log transformation will be applied to the data so that the assumptions are satisfied.

Where there is a significant main effect of *Time* but no significant *Condition* x *Time* interaction, each subsequent time point will be compared against 'Baseline' using a pooled mean from the three groups using Dunnett's test. If the *Condition* x *Time* interaction is significant, within each group, each time point will be compared against baseline using a Dunnett's test and groups will be compared to each other at all time points using the Student Newman-Keuls (SNK) test.

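### CTX and P1NP drawn at 15 and 45 minutes of running are compared with rest without any check on plasma volume: a secondary issue, mainly for P1NP

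*Combined protocol and SAP*

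**What the plan says.** Section 6.3 collects blood at baseline, "immediately pre-exercise, and after 15 minutes and 45 minutes of exercise and after 2-hours of recovery". Section 6.4.3 sets the exercise: "Participants will perform 45 min of treadmill running at 70" per cent of VO2max, on a downhill slope. Section 6.8 places the later blood samples at "15 minutes during exercise, 45 minutes (immediately post-exercise) and 2 hours post-exercise", with the same timings in the breakfast-only arm. Two of the five samples are therefore drawn during the run or at the moment it ends.

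Section 6.3 states how the result will be read: "The osteogenic response to exercise will be determined by measuring a marker of bone formation; P1NP and a marker of resorption; CTX-1". Sections 6.4.5 and 6.4.6 name serum-separator tubes only. The other analytes are covered by "Measurement of glucose, insulin, and cortisol will be done at the Chemical Chemistry laboratory". The text available lists no haematocrit, haemoglobin, albumin, total protein or plasma-volume correction, and does not state posture at sampling or fluid intake during the visit.

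The mixed model in section 6.9 has condition, time point and participant as its terms. If the interaction is significant, "within each group, each time point will be compared against baseline using a Dunnett's test", and the conditions are compared with one another at every time point by SNK. If only time is significant, each time point is compared with baseline using a mean pooled over the three conditions.

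The first objective in Section 4 is "To compare the effect of exercise on bone turnover markers before and after the meals" after an overnight fast. Section 6.2 defines the primary outcome as the change in CTX from pre-exercise to 2 hours post-exercise, fasted-exercised against fed-exercised.

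**The concern.** CTX and P1NP are measured as concentrations. If running moves water out of plasma while the marker stays in it, the concentration rises although bone has released nothing more. Two planned comparisons carry that rise in full: 15 or 45 minutes against 8.30am within a running condition, and a running condition against breakfast-only at the same time. The breakfast-only arm controls for the meal and the time of day. It rests throughout, so it cannot remove a shift caused by the run.

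P1NP is the more exposed marker. Section 5.1 describes bone formation markers as largely unresponsive to both exercise and feeding, so a modest uniform rise could be the whole of a reported effect. For CTX in the FED condition, section 5.1 expects feeding to lower the marker by about half after 2-3 hours; there a fluid shift would hide part of a fall. Section 6.3 also uses cortisol to help interpret bone-marker changes, and a shift that raises cortisol and the bone markers together could look like a hormonal association.

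**Working it through.** **Inputs from the documents (section 6.2).** Difference 0.168 µg/l, described as 30%; SD 0.2 µg/l; two-sided 2.5% level; 80% power; 16 participants including 2 for withdrawals.

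**The plan's own figure.** Paired normal approximation: n = (0.2 × (2.241 + 0.842) / 0.168)² = 13.47, rounded up to 14; 14 + 2 = 16. The figure reproduces. It gives 14 completers, and an implied reference CTX of 0.168 / 0.30 = 0.56 µg/l.

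**Inputs that are assumed.** Plasma-volume fall x of 5-10%, with the marker fully retained in plasma. SD of the within-visit change of 6-12% of baseline, with 20% as a wider case. The documents give neither.

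**Step 1: apparent rise.** Rise = 1/(1 − x) − 1.
- x = 5%: 5.3%
- x = 8%: 8.7%
- x = 10%: 11.1%

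For CTX at 0.56 µg/l, falls of 5% and 10% add 0.029 and 0.062 µg/l, which is 18% and 37% of 0.168 µg/l.

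**Step 2: chance of a false significant result at one exercise time point.** Paired t-test, n = 14, 13 df, two-sided level 0.05/4 = 0.0125 (a Bonferroni stand-in for Dunnett with four comparisons), critical t = 2.896, noncentrality = rise × √14 / SD. Example: 5.26 × 3.742 / 8 = 2.46, giving 37%. The documented CTX SD is 0.2/0.56 = 35.7% of the reference value.

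| SD of change | x = 5% | x = 8% | x = 10% |
|---|---|---|---|
| 6% | 65% | 99% | >99% |
| 8% | 37% | 86% | 98% |
| 12% | 15% | 46% | 71% |
| 20% | 5% | 15% | 25% |
| 35.7% (CTX, 0.2 µg/l) | 2% | 5% | 7% |

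With no shift the rate would be 1.25%. Bonferroni is conservative: with a simulated Dunnett critical value of about 2.52 on 52 df, the SD 8% row becomes 48%, 94% and >99%.

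**Step 3: the testing sequence.** The table applies only if the within-condition test is reached, which requires a significant interaction. A rise in both running conditions against a flat resting one is itself an interaction pattern, so the shift can help to open that route. If the interaction is not significant, the pooled mean contains one resting condition of three and the shift falls to two-thirds. With the same SD assumed for the pooled change, the SD 8% row becomes 15%, 46% and 71%, the 20% row 3%, 6% and 10%, and the CTX row 2%, 3% and 4%.

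**Step 4: comparisons that are spared.** If FAST and FED share the same fall x, both means are multiplied by 1/(1 − x). No difference is created where there is none, and a true one is scaled by 1.053-1.111. The primary outcome uses neither exercise-time sample. Only a residual FAST-FED difference in plasma volume at 2 hours could reach it: an assumed 1-3% is 0.006-0.017 µg/l, or 3-10% of 0.168 µg/l.

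**The case against.** The strongest reply concerns reach. The research question and the first objective are about exercise taken fasted versus fed. Both of those conditions run, so a common shift largely cancels. A reader might infer that the primary CTX result is compromised, or that the first objective cannot be answered; the documents do not support either, because the primary samples are at pre-exercise and 2 hours and the contrast is between two running arms. That part of the reply stands.

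The second reply concerns size. Both inputs to the high probabilities are assumed. The only SD in the documents, 0.2 µg/l for CTX, gives 2-7%. That SD may not describe a change over minutes within one visit, but no other is available, and none is given for P1NP. A reader might also infer that CTX will be reported as falsely raised in every running condition; in FED the expected direction is downward, so masking is the likelier error. These limits stand too.

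Third, section 6.3 collects urine before and after exercise and says that samples will be analysed later for bone markers. Whether that covers urine is unclear, the measurement schedule in 6.8.2 omits it, and section 6.9 gives it no role, so it is not a planned correction.

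Finally, moving all exercise-versus-rest claims to 2 hours against 8.30am would leave feeding and time of day in the contrast. That is correct, and the fix avoids it.

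**Conclusion.** The point holds as a secondary issue, mainly for P1NP. As planned, the exercise-versus-rest comparisons at 15 and 45 minutes cannot tell a fluid shift from a change in bone turnover, and the breakfast-only arm does not help with that. The size is uncertain. An assumed 5-10% fall in plasma volume gives a 5.3-11.1% apparent rise. The chance of declaring it significant runs from a few per cent to near certainty, according to an SD that the plan does not state and to which Dunnett test applies. The calculation also assumes that the marker does not leave plasma with the water. The sample size is unaffected, and nothing here invalidates the primary outcome or the FAST-versus-FED question.

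**What to change.** Before samples are analysed, add total protein or albumin at every draw, on the serum already collected. In section 6.9, state that for the exercise-versus-rest comparisons at 15 and 45 minutes CTX and P1NP will be reported both unadjusted and relative to protein, and that an exercise effect at those times will be claimed only where the two agree. Requiring agreement matters because protein adjustment itself assumes that protein stays in plasma.

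If the assay is not done, label those comparisons descriptive and uncorrected. Base the exercise-versus-rest claim on FED-exercised versus breakfast-only at the 2-hour time point. Both conditions have the same breakfast at the same time, so feeding and time of day are balanced, which they are not for 2 hours against 8.30am. Any shift persisting at 2 hours would remain unmeasured.

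Cost: one routine assay on existing serum and a few sentences in 6.9, or else no formal exercise-versus-rest claim at two secondary time points. Visits, blood draws, exercise and sample size do not change.
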